6.7.2.2 Management of nausea and vomiting

Events of nausea and vomiting are known to be associated with olaparib treatment. In study D0810C00019, nausea was reported in 71% of the olaparib treated subjects and 36% of the placebo treated subjects, and vomiting was reported in 34% of the olaparib treated subjects and 14% of the placebo treated subjects. These events are generally mild to moderate (CTCAE grade 1 or 2) in severity, intermittent, and manageable on continued treatment. The first onset generally occurs in the first month of treatment for nausea and within the first 6 months of treatment for vomiting. For nausea, the incidence generally plateaus around 9 months and for vomiting around 6 to 7 months.

No routine prophylactic anti-emetic treatment is required at the start of study treatment; however, subjects should receive appropriate anti-emetic treatment at the first onset of nausea or vomiting and as required thereafter, in accordance with local treatment practice guidelines. Alternatively, olaparib tablets can be taken with a light meal/snack (i.e., 2 pieces of toast or a couple of biscuits). Note: For adverse events of nausea and vomiting, an additional eCRF is required.

As per international guidance on anti-emetic use in cancer subjects (European Society for Medical Oncology, National Comprehensive Cancer Network), generally a single agent anti-emetic should be considered, e.g., dopamine receptor antagonist, antihistamines, or dexamethasone.

6.7.2.3 Renal impairment

If subsequent to study entry and while still on study therapy, a subject's estimated creatinine clearance (CrCl) decreases to become < 51 mL/min, retesting should be performed promptly.

A dose reduction is recommended for subjects who meet the following criteria during the course of the study:

- Baseline $CrCl \ge 51 \text{ mL/min}$ who have on study a CrCl < 51 mL/min,
- Baseline CrCl < 51 mL/min but had serum creatinine $\le 1.5 \times ULN$, and then on study had a clinically meaningful lower CrCl value.

CCI

Olaparib has not been studied in subjects with severe renal impairment ($CrCl \le 30 \text{ mL/min}$) or end-stage renal disease; if subjects develop severe impairment or end-stage renal disease olaparib must be discontinued.

6.7.2.4 Interruptions for intercurrent non-toxicity related events

Study treatment dose interruption for conditions other than toxicity resolution should be kept as short as possible. If a subject cannot restart study treatment within 4 weeks for resolution of intercurrent conditions not related to disease progression or toxicity, the case should be discussed with the AstraZeneca Representative Study Physician. See Section 6.7.

All dose reductions and interruptions (including any missed doses), and the reasons for the reductions/interruptions, are to be recorded in the eCRF.

Study treatment should be stopped at least 3 days prior to planned surgery. After surgery, study treatment can be restarted when the wound has healed. No stoppage of study treatment is required for any needle biopsy procedure.

Study treatment should be discontinued for a minimum of 3 days before a subject undergoes palliative radiation treatment. Study treatment should be restarted within 4 weeks as long as any bone marrow toxicity has recovered.

[figure not shown]
Because the adverse events related to olaparib may include asthenia, fatigue, and dizziness, subjects should be advised to use caution while driving or using machinery if these symptoms occur.

6.8 Study governance and oversight

A Study Steering Committee composed of representatives from AstraZeneca and key Investigators/scientific advisors will be responsible for providing recommendations to US Medical Affairs leadership at AstraZeneca based on Investigator input, review, and oversight of study execution, scientific conduct, and analysis of study data. The accountabilities and

CCI

requirements of the Steering Committee members will be outlined in the Steering Committee Charter.

7.2 Dose and treatment regimens

Each dosing container will contain sufficient medication for at least 28 days plus overage.

Sufficient study treatment should be dispensed for at least each treatment period plus overage; however, additional treatment can be dispensed to subjects to last longer in accordance with local practice.

CCI

The tablets should be swallowed whole and not chewed, crushed, dissolved, or divided. Olaparib can be taken with or without food.

If vomiting occurs shortly after the olaparib tablets are swallowed, the dose should only be replaced if all of the intact tablets can be seen and counted. Should any subject enrolled in the study miss a scheduled dose for any reason (e.g., as a result of forgetting to take the tablets or vomiting), the subject will be allowed to take the scheduled dose up to a maximum of 2 hours after that scheduled dose time. If greater than 2 hours after the scheduled dose at the next scheduled time.

Subjects will continue with olaparib tablets 300 mg CC, the second secon

Once subjects have been discontinued from the active treatment period of the study, other treatment options during the survival follow-up period will be at the discretion of the

Investigator. Subjects who continue to gain clinical benefit are allowed to continue olaparib post-study completion. AstraZeneca will continue to supply olaparib tablets after completion of this study until olaparib tablets are approved and commercially available and subjects will then be transferred to commercially available olaparib tablets.

Dose Reductions

For guidance on dose reductions for management of adverse events, refer to Section 6.7.

For guidance on dose reductions when concomitant strong or moderate CYP3A inhibitors cannot be avoided, see Section 7.7.

7.3 Labeling

Labels will be prepared in accordance with Good Manufacturing Practice (GMP) and local regulatory guidelines. The labels will fulfill GMP Annex 13 requirements for labeling. Label text will be translated into local language.

7.4 Storage

All study drugs should be kept in a secure place under appropriate storage conditions. The olaparib label on the bottle specifies the appropriate storage.

7.5 Compliance

The administration of all study medications (including olaparib) should be recorded in the appropriate sections of the eCRF.

Subjects should be given clear instructions on how and when to take their study treatment. Subjects will self-administer olaparib. Study site staff will perform tablet counts at regular intervals during treatment. Compliance will be assessed by the tablet count, and the information will be recorded in the appropriate section of the eCRF. After the tablet count has been performed, the remaining tablets will not be returned to the subject but will be retained by the investigative site until reconciliation is completed by the study monitor. All subjects must return their bottle(s) of olaparib at the appropriate scheduled visit, when a new bottle will be dispensed. Subjects will be instructed to notify study site personnel of missed doses.

Subjects must return all containers and any remaining tablets at the end of the study.

7.6 Accountability

The study drug provided for this study will be used only as directed in the Clinical Study Protocol.

The study site personnel or study monitor will account for olaparib received at the site, unused study drugs, and for appropriate destructions. Certificates of delivery, destruction, or return should be signed.

Study drug will not be distributed to the study site until the contract is concluded between the study site and the AstraZeneca Representative. The IP Storage Manager is responsible for managing the study medication from receipt by the study site until the return of all unused study medication to the AstraZeneca Representative. AstraZeneca will provide the study documents 'Procedures for drug accountability' and 'Procedures for drug storage,' which describe the specific requirements. The Investigator(s) is responsible for ensuring that the subject has returned all unused study medication.

7.7 Concomitant and other treatments

The use of any natural/herbal products or other traditional remedies should be discouraged, but use of these products, as well as use of all vitamins, nutritional supplements, and all other concomitant medications must be recorded in the eCRF.

Medications that may NOT be administered

No other anti-cancer therapy (chemotherapy, immunotherapy, hormonal therapy [hormone replacement therapy is acceptable], radiotherapy, biological therapy, or other novel agent) is to be permitted while the subject is receiving study medication.

Live virus and live bacterial vaccines should not be administered whilst the subject is receiving study medication and during the 30-day follow-up period. An increased risk of infection by the administration of live virus and bacterial vaccines has been observed with conventional chemotherapy drugs and the effects with olaparib are unknown.

Restricted concomitant medications

Strong or Moderate CYP3A inhibitors

Known strong CYP3A inhibitors (e.g., itraconazole, telithromycin, clarithromycin, boosted protease inhibitors, indinavir, saquinavir, nelfinavir, boceprevir, telaprevir) or moderate CYP3A inhibitors (ciprofloxacin, erythromycin, diltiazem, fluconazole, verapamil) should not be taken with olaparib.

If there is no suitable alternative concomitant medication, then the dose of olaparib should be reduced for the period of concomitant administration. The dose reduction of olaparib should be recorded in the CRF with the reason documented as concomitant CYP3A inhibitor use.

- Strong CYP3A inhibitors reduce the dose of olaparib to 100 mg *bid* for the duration of concomitant therapy with the strong inhibitor and for 5 half-lives afterwards.
- Moderate CYP3A inhibitors reduce the dose of olaparib to 150 mg *bid* for the duration of concomitant therapy with the moderate inhibitor and for 3 half-lives afterwards.

After the washout of the inhibitor is complete, the olaparib dose can be re-escalated.

Strong or Moderate CYP3A inducers

Strong (e.g., phenobarbital, phenytoin, rifampicin, rifabutin, rifapentine, carbamazepine, nevirapine, enzalutamide, and St John's Wort) and moderate CYP3A inducers (e.g., bosentan, efavirenz, modafinil) of CYP3A should not be taken with olaparib.

If the use of any strong or moderate CYP3A inducers are considered necessary for the subject's safety and welfare, this could diminish the clinical efficacy of olaparib.

If a subject requires use of a strong or moderate CYP3A inducer then they must be monitored carefully for any change in efficacy of olaparib.

P-gp inhibitors

It is possible that co-administration of P-gp inhibitors (e.g., amiodarone, azithromycin) may increase exposure to olaparib. Caution should therefore be observed.

Effect of olaparib on other drugs

Based on limited in vitro data, olaparib may increase the exposure to substrates of CYP3A4, P-gp, OATP1B1, OCT1, OCT2, OAT3, MATE1, and MATE2K.

Based on limited in vitro data, olaparib may reduce the exposure to substrates of CYP3A4, 2B6, 2C9, 2C19, and P-gp.

The efficacy of hormonal contraceptives may be reduced if co-administered with olaparib.

Caution should therefore be observed if substrates of these isoenzymes or transporter proteins are co-administered.

Examples of substrates include:

- CYP3A4 hormonal contraceptive, simvastatin, cisapride, cyclosporine, ergot alkaloids, fentanyl, pimozide, sirolimus, tacrolimus and quetiapine
- CYP2B6 bupropion, efavirenz
- CYP2C9 warfarin
- CYP2C19 lansoprazole, omeprazole, S-mephenytoin
- P-gp simvastatin, pravastatin, digoxin, dabigatran, colchicine
- OATP1B1 bosentan, glibenclamide, repaglinide, statins, valsartan

- OCT1, MATE1, MATE2K metformin
- OCT2 serum creatinine
- OAT3 furosemide, methotrexate

Anticoagulant therapy

Oral anticoagulants are permitted. Subjects who are taking warfarin may participate in this study; however, it is recommended that INR be monitored carefully at least once per week for the first month, then monthly thereafter, if the INR is stable. For Coumadin-like agents, prothrombin time should be checked at baseline and followed closely (as clinically indicated). Subcutaneous heparin and low molecular weight heparin are permitted.

Anti-emetics/Anti-diarrheals

From screening onwards, should a subject develop nausea, vomiting, and/or diarrhea, then these symptoms should be reported as adverse events (see Section 6) and appropriate treatment of the event should be given.

Palliative radiotherapy

Palliative radiotherapy may be used for the treatment of pain at the site of bony metastases that were present at baseline, provided the Investigator does not feel that these are indicative of clinical disease progression during the study period. Study treatment should be discontinued for a minimum of 3 days before a subject undergoes therapeutic palliative radiation treatment. Study treatment should be restarted within 4 weeks as long as any bone marrow toxicity has recovered (i.e., if a subject has not recovered from bone marrow toxicity within 4 weeks they should be discontinued from the study).

Administration of other anti-cancer agents

Subjects must not receive any other concurrent anti-cancer therapy, including investigational agents, while on study treatment. Subjects may continue the use of bisphosphonates or denosumab for bone disease and corticosteroids for the symptomatic control of brain metastases provided the dose is stable before and during the study and they were started at least 4 weeks prior to beginning study treatment.

Subsequent therapies for cancer

Details of first and subsequent therapies for cancer and/or details of surgery for the treatment of the cancer, after discontinuation of treatment, will be collected until database lock for ORR. Reasons for starting subsequent anti-cancer therapies, including access to other PARP inhibitors or investigational drugs, will be collected until database lock for ORR.

7.7.1 Other concomitant treatment

Medications other than those described above, which are considered necessary for the subject's safety and wellbeing, may be given at the discretion of the Investigator and recorded in the appropriate sections of the eCRFs.

In addition, any unplanned diagnostic, therapeutic, or surgical procedure performed during the study period must be recorded in the eCRFs.

7.8 Post-study access to study treatment

Subjects are permitted to continue to receive olaparib beyond the closure of the study efficacy database if, in the opinion of the Investigator, they are continuing to receive benefit from treatment with olaparib. During this time, AESIs and SAEs must still be collected and reported until 30 days after the subject finally stops taking olaparib.

Subjects will be followed-up for survival assessments every 12 weeks following disease progression. See Section 4.4.

Subsequent anti-cancer treatment is expected to be initiated following cancer recurrence or development of a new cancer. Information on subsequent PARP inhibitors or other cancer therapies (therapies given, not duration or clinical outcomes) should be recorded in the appropriate eCRFs.

8. STATISTICAL ANALYSES

8.1 Statistical considerations

• All statistical analyses will be performed by AstraZeneca or its representatives.

A comprehensive Statistical Analysis Plan (SAP) will be prepared and any subsequent amendments will be documented, with final amendments completed prior to database lock. Data will be summarized for all subjects who have received at least 1 dose of olaparib and will be presented by cohort.

[figure not shown]
8.2 Sample size estimate

This is a non-comparative Phase II study and each of the 4 cohorts will be analyzed separately; no statistical comparison will be made between the cohorts.

Olaparib, administered as monotherapy to date, has reported ORRs in genetic BRCAm ovarian cancer in excess of 30%. A Forest plot of ORR across all monotherapy studies of olaparib (capsules formulation) is shown in Figure 4.

[figure not shown]

Responders are patients having a best objective response of complete response or partial response.

Note: In all studies shown above except Study D0810C00019 (Study 19), *BRCA* mutation status was based on assessment of *gBRCA* mutation status only.

bd = twice daily; CI = confidence interval; gBRCA = germline BRCA; ORR = objective response rate.

8.3 Definitions of analysis sets

Table 13 provides a summary of outcome variables and analysis populations.

Table 13	Summary of Outcome Variables and Analysis Populations
Lable 15	Summary of Outcome variables and Analysis i opulations

Outcome Variable	Population		
Efficacy Data			
- Primary: ORR	Efficacy		
- Secondary: DoR, CA-125 RR ^a , DCR, PFS, TTAP, OS, HRRm	Efficacy		
- Demography	Safety		
Safety Data			
- Adverse events	Safety		
- Laboratory measurements	Safety		
- Vital signs	Safety		

a. CA-125 RR will be analyzed on a subset of the efficacy analysis set (i.e., excluding subjects whose baseline CA-125 level is not ≥ 2 × ULN and/or not assessed within 2 weeks of starting treatment with olaparib).

CA = Cancer antigen; CA-125; CA-125 RR = CA-125 response rate; DCR = disease control rate; DoR = duration of response; HRRm = homologous recombination repair mutation; ORR = objective response rate;

OS = overall survival; PFS = progression-free survival; RECIST = Response Evaluation Criteria in Solid Tumors; TTAP = time to any progression (earliest of CA-125, RECIST, or death); ULN = upper limit or normal.

8.3.1 Efficacy analysis set

The efficacy analysis set comprises all subjects who received at least 1 dose of olaparib and had a baseline tumor assessment.

8.3.2 Safety analysis set

The safety analysis set comprises all subjects who received at least 1 dose of olaparib.

8.4 Outcome measures for analyses

8.4.1 Calculation or derivation of efficacy variable(s)

At each visit, subjects will be assigned a visit response of CR, PR, SD, PD, or not evaluable (NE) based on RECIST v1.1 guidelines, based on the Investigator's assessment.

8.4.2 Primary endpoint

The ORR rate is defined as the percentage of subjects with measurable disease with at least 1 visit response of CR or PR that is confirmed at least 4 weeks later. Data obtained up until progression, or last evaluable assessment in the absence of progression, will be included in the assessment of ORR. However, any CR or PR that occurred after a further anti-cancer therapy was received will not be included in the numerator for the ORR calculation. Subjects lacking valid data to assign a response status will be included in the denominator for the response rate calculation based on the efficacy analysis set.

In the case where a subject has 2 non-consecutive visit responses of PR, then, as long as the time between the 2 visits of PR is greater than 4 weeks and there is no PD between the PR visits, the subject will be defined as a responder. Similarly, if a subject has visit responses of CR, NE, CR, then as long as the time between the 2 visits of CR is greater than 4 weeks, a best response of CR will be assigned.

8.4.3 Secondary endpoints

8.4.3.1 Duration of response

The DoR will be defined as the time from the date of first documented response (that is subsequently confirmed) until the date of documented objective PD or death in the absence of PD. The end of response should coincide with the date of PD or death from any cause used for the PFS endpoint. The time of the initial response will be defined as the latest of the dates contributing towards the first visit response of PR or CR. If the response is not confirmed (per RECIST v1.1), it will not be included. If a subject does not progress following a response, then the subject's DoR will use the PFS censoring time.

8.4.3.2 CA-125 response rate

The CA-125 response will be based upon the latest GCIG guidelines. Serum samples will be collected for CA-125 tumor markers on all subjects at baseline (within 2 weeks prior to Cycle 1, Day 1), Day 1 of each cycle, and at the End-of-Study Treatment Visit.

A response according to CA-125 has occurred if there is at least a 50% reduction in CA-125 levels from the baseline sample. The response must be confirmed and maintained for at least 28 days. Subjects can be evaluated according to CA-125 only if they have a baseline sample that is at least twice the ULN and within 2 weeks prior to starting treatment.

Those subjects who have both a CA-125 response and whose CA-125 level falls to within the normal range, can be classified as CA-125 complete responders.

The CA-125 response rate is defined as the percentage of subjects achieving a CA-125 response. The CA-125 CR Rate is defined as the percentage of subjects achieving a CA-125 response with the CA-125 level additionally falling within the normal range. The CA-125 response rate will be analyzed on a subset of the efficacy analysis set (i.e., excluding subjects whose baseline CA-125 level is not $\geq 2 \times$ ULN and/or not assessed within 2 weeks of starting treatment with olaparib) (Rustin et al 2011).

8.4.3.3 Disease control rate

The DCR is defined as the percentage of subjects who have a best overall response of confirmed CR or PR or SD at ≥ 8 weeks divided by the number of subjects in the efficacy analysis set, prior to any PD event.

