2.2 Secondary objectives

Secondary Objectives:	Outcome Measures:
To determine the clinical effectiveness of olaparib treatment in each of 4 cohorts assessed using: • DoR, • CA-125 response rate, • DCR	• DoR, for those subjects with a confirmed response of CR or PR, response duration will be measured from the date of the measurement criteria for CR or PR are first met until the date of documented objective progression or death in the absence of disease progression.
 PFS, TTAP, OS, and 	• CA-125 response rate, defined as the percentage of subjects with a CA-125 response according to GCIG criteria divided by the number of subjects evaluable for CA-125 response.
HRRm gene panel status related to clinical outcome.	• DCR, defined as the percentage of subjects with a best overall response of confirmed CR or PR (at any time up to and including the defined analysis cut-off point) or who have demonstrated stable disease (SD) for at least 8 weeks from first dose, divided by the number of subjects in the efficacy analysis set.
	• PFS, defined as the time from the date of the first dose of olaparib to the earlier date of assessment of objective progression (per RECIST v1.1 criteria) or death by any cause in the absence of progression.
	• TTAP, defined as the time from the date of the first dose of olaparib to the earlier date of CA-125 progression (GCIG criteria) or RECIST v1.1 progression, or death by any cause in the absence of progression.
	• OS, defined as the time from the date of the first dose of olaparib to the date of death from any cause.
	• HRD status as per HRRm gene panel assessment (positive or negative) will be correlated with clinical outcome (ORR, defined above) for subjects enrolled in the 2 cohorts with BRCAwt (cohorts 3 and 4).

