- k. Coagulation tests are only required if clinically indicated. For a list of all required laboratory tests, please refer to Section 5.2.1. All enrolled subjects will have safety blood samples taken weekly during the first month on treatment followed by monthly assessments until discontinuation of study treatment. Safety blood samples will be taken at the 30-day Follow-up Visit as well.
- 1. Women of childbearing potential must have a negative urine or serum pregnancy test within 28 days prior to starting treatment and a confirmatory test on Day 1 before initiating olaparib treatment; and at the timepoints shown in Table 6 during study treatment, and at the 30 day follow up visit. Pregnancy testing for women of childbearing potential should be conducted at regular intervals (eg, monthly). If results are positive, the subject is ineligible/must be discontinued from the study.
- m. Subjects with an unknown gBRCA status will have their blood and tumor tested with the myChoice[®] HRD and BRACAnalysis CDx[®] in parallel at pre-screening (if consented) or at screening, if not previously performed by Myriad during pre-screening.
- n. Subjects with known gBRCA status from the local laboratory must provide a blood and tumor sample at screening for confirmatory purposes. Their involvement in the study will not be affected by the result of the Myriad test.
- CA-125 will be tested at baseline and every month thereafter until objective disease progression, based on progressive serial elevation of serum CA-125 according to the modified GCIG criteria. Samples should be taken pre-dose at Visit 2.
- p. RECIST assessments will be performed using CT/MRI of the chest, abdomen, and pelvis, with other regions as clinically indicated for the assessment of disease, no more than 28 days prior to study treatment start and as close as possible to the start of study treatment. A CT examination with intravenous contrast media administration is the preferred method. An MRI should be used where CT is not feasible or it is medically contraindicated.

Date 10 October 2017

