5.1 Efficacy assessments

5.1.1 CT and MRI scans tumor assessments (RECIST v1.1)

The baseline tumor assessment will be performed no more than 28 days prior to study treatment start (Visit 2) and as close as possible to study treatment start. Following the

baseline tumor assessment, subsequent tumor assessments according to RECIST v1.1 should be performed at the end of every 8 weeks (\pm 1 week) from first dose of study drug (Visit 2) for 48 weeks and every 12 weeks (\pm 1 week) (relative to the date of enrollment) thereafter until PD. If an unscheduled assessment was performed and the subject has not progressed, every attempt should be made to perform the subsequent assessments at their scheduled visits. Subjects who are determined to have PD according to RECIST v1.1 criteria (including confirmatory RECIST scan) by the Investigator may have additional scans performed per the site's standard of care. All treatment decisions will be based on the Investigator's assessment of the scans.

A copy of all tumor assessment scans will be collected by an AstraZeneca Representative through disease progression.

All subjects should have RECIST assessments until documented evidence of objective radiological progression in accordance with RECIST v1.1, irrespective of treatment decisions (i.e., RECIST follow-up until progression even if a subject discontinues study treatment prior to progression and/or receives a subsequent therapy prior to progression).

At baseline, the imaging modalities used for RECIST assessment will be CT (MRI where CT is contraindicated) scans of the chest, abdomen, and pelvis, with other regions as clinically indicated for the assessment of disease. Follow-up CT or MRI assessments (per RECIST v1.1) will be by chest (in those subjects with disease in the chest or upper abdomen lymphadenopathy at baseline), abdomen, and pelvis, with any other regions imaged at baseline where disease was present. Any other sites at which new disease is suspected should also be appropriately imaged. The methods of assessment of tumor burden used at baseline must be used at each subsequent follow-up assessment. A CT examination with intravenous contrast media administration is the preferred method. An MRI should be used where CT is not feasible or it is medically contraindicated. For brain lesion assessment, MRI is the preferred method. Subjects must be followed-up until RECIST disease progression.

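### The DCR definition has no cut at subsequent anti-cancer therapy, unlike ORR, so disease control reached on the next treatment can be credited to olaparib; CA-125 response carries a smaller risk of the same kind

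*Protocol*

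**What the plan says.** For the primary endpoint, Section 8.4.2 deals with subsequent therapy directly: "any CR or PR that occurred after a further anti-cancer therapy was received will not be included in the numerator for the ORR calculation". Subjects without valid response data stay in the denominator.

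For DCR, Section 8.4.3.3 gives the "percentage of subjects who have a best overall response of confirmed CR or PR or SD at ≥ 8 weeks". Its denominator is the efficacy analysis set, and its only limit is that the outcome must come before progression. Section 2.2 words it slightly differently. Confirmed CR or PR counts "at any time up to and including the defined analysis cut-off point", and the stable-disease part is set apart as subjects "who have demonstrated stable disease (SD) for at least 8 weeks from first dose". Neither version mentions further anti-cancer therapy.

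Scans go on after a switch. Section 5.1.1 requires "RECIST follow-up until progression even if a subject discontinues study treatment prior to progression and/or receives a subsequent therapy prior to progression".

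For CA-125, Section 8.4.3.2 states: "A response according to CA-125 has occurred if there is at least a 50% reduction in CA-125 levels from the baseline sample". The fall must be confirmed and held for at least 28 days. Again there is no rule on subsequent therapy. The CA-125 footnote to Table 6 says "CA-125 will be tested at baseline and every month thereafter until objective disease progression".

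**The concern.** DCR and CA-125 response rate are secondary measures of how well olaparib works in each of four uncontrolled cohorts. Section 3.9 allows subjects to stop olaparib without progression, for example for an adverse event or by their own decision. Section 1.1 says that most platinum-sensitive subjects respond again to platinum, so the next treatment is likely to be active. If assessments made on that treatment count, part of its effect is reported as olaparib's. With no comparator arm, nothing offsets this. The endpoints would also disagree on the same subject: a response seen after the switch is barred from ORR, yet stable disease seen after the switch would count toward DCR.

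**Working it through.** The plan gives no DCR, no CA-125 response rate and no rate of subsequent therapy, so there is no figure to reproduce. The check is a comparison of passages.

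**Step 1. Rule for data after a further anti-cancer therapy, by endpoint**
- ORR (8.4.2): excluded from the numerator, explicitly.
- PFS (8.4.3.4): included, explicitly.
- DCR (8.4.3.3 and 2.2): no rule; the only limits are progression and the data cut-off.
- CA-125 response (8.4.3.2): no rule.

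**Step 2. One hypothetical subject under the DCR text.** She stops olaparib in week 3 without progression, starts another therapy in week 5, and has stable disease at the week-8 scan required by Section 5.1.1.
- Section 8.4.3.3: stable at 8 weeks with no earlier progression, so she counts.
- Section 2.2: stable for 8 weeks measured from first dose, so she counts. Nothing requires her to be on olaparib or free of new therapy.
- Section 8.4.2: its exclusion concerns CR and PR only and does not reach stable disease.
- Appendix G: best overall response closes at the end of treatment. She has no post-baseline scan by then, so she does not count.

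The document gives two answers for the same subject.

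**Step 3. Who is affected.** A subject who switches after an evaluable, non-progressed scan at 8 weeks or later is already a DCR success, whatever happens next. A response reached after a later switch adds nothing. DCR status can change only for subjects who switch before they have such a scan. This is why the gap matters most for stable disease at the first scan.

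**Step 4. CA-125 sampling passages side by side**
- Stopping at discontinuation: Section 8.4.3.2 lists no sample after the end-of-treatment visit; the Table 6 grid marks the discontinuation visit and leaves the 30-day follow-up blank; Table 8 counts a sample at the discontinuation visit only.
- Continuing: the Table 6 footnote runs monthly testing to objective progression; Section 5.2.1.4 evaluates subjects until RECIST progression; Section 4.3.1 follows CA-125 after the last dose, per site standards.

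No passage says that CA-125 testing continues once a new therapy has started. If values are recorded, nothing excludes them, and the 28-day confirmation could also fall after the switch.

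**Step 5. Direction.** Both endpoints record whether success was ever reached. Extra assessments after a switch can add a success but cannot remove one already achieved, so the bias can only be upward.

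**Step 6. Size per subject.** The change in DCR from reclassifying k subjects is 100 × k / n points. For k = 1:
- n = 30 (cohort minimum): 100 × 1/30 = 3.3 points.
- n = 90 (cohort maximum): 100 × 1/90 = 1.1 points.

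The value of k cannot be obtained from the documents.

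**The case against.** The strongest reply is Appendix G. DCR rests on best overall response, Appendix G ends that at the end of treatment, and Section 7.7 bars other anti-cancer therapy during olaparib. Read that way, post-switch scans never count. This stands far enough that one cannot say such outcomes *will* be credited to olaparib, only that they *can* be. It does not close the gap. Section 2.2 runs CR and PR to the data cut-off and words stable disease separately from best overall response. The same paragraph of Appendix G says that no confirmation is required, which contradicts Section 8.4.2. And if Appendix G governed, the exclusion in 8.4.2 would be largely redundant.

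Second, the CR/PR part of DCR uses the same terms as ORR and arguably inherits its rule. That is fair, and it leaves stable disease as the clear gap, in the narrow group identified in Step 3.

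Third, a reader might infer that CA-125 response has the same defect as DCR. The documents do not support that: three of the sampling passages stop at discontinuation, and Section 5.1.1 extends follow-up past a new therapy for RECIST only. What remains is an unresolved conflict between passages.

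Fourth, endpoints may legitimately treat subsequent therapy differently, as PFS does. But PFS states its choice, and DCR does not.

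Fifth, the SAP may settle the data window. Only the protocol is considered here. Even so, the protocol itself fixes the DCR definition and writes the ORR rule in the same part of Section 8.4, so the definition should be right there.

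**Conclusion.** The point holds for DCR. As written in Sections 8.4.3.3 and 2.2, disease control first shown after a switch can be counted for olaparib, most clearly stable disease at 8 weeks or later from first dose. Appendix G points the other way and no rule decides between them. For CA-125 response the risk is smaller and depends on which sampling passage sites follow.

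The bias is upward. It affects secondary, descriptive endpoints and does not touch ORR or the futility rule. Each reclassified subject is worth 3.3 points of DCR at n = 30 and 1.1 points at n = 90. It may be tempting to turn this into an expected overstatement by assuming a switching rate, or by using the response range of 17% to 79% for platinum re-treatment in Section 1.2. The documents do not support either: they give no switching rate, and that range is not a CA-125 response rate.

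**What to change.** - In Section 8.4.3.3, and in the matching text of Section 2.2 and the synopsis, state that only RECIST assessments made before the start of any further anti-cancer therapy count toward stable disease at 8 weeks or later and toward CR or PR. Subjects with no qualifying assessment stay in the denominator as not controlled. This goes beyond copying 8.4.2, whose exclusion covers CR and PR only.
- In Section 8.4.3.2, apply the same cut to CA-125 values and keep such subjects among those evaluable, as not responding.
- Reconcile the best-overall-response window in Appendix G with the cut-off wording in Section 2.2.
- Reconcile the CA-125 sampling passages: Section 8.4.3.2, the Table 6 grid and footnote, Table 8, and Sections 4.3.1 and 5.2.1.4.

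The cost is a few sentences and no new data, since Section 7.7 already has subsequent therapy recorded until the ORR database lock. The downside is a slightly lower reported DCR and CA-125 response rate.
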